in a 12HR combination since both isoniazid and rifapentine can damage the liver; CDC is calling for studies of 12HR in prisoners, but have not yet funded research. In the absence of studies of 12HR use in prisoners, it is crucial to assess both completion rates and tolerability (especially when high HCV prevalence is present).

Eligibility for Part B includes:

- 1) Meets inclusion criteria for Part A
- 2) Has latent TB (HIV+, or TST \geq 10mm (HIV-)) and no active TB disease
- 3) \geq 6 months before end of sentence to ensure option for treatment completion
- 4) AST/ALT <5 ULN, or AST/ALT <3 x ULN if TBil >2 x ULN
- 5) Not on a protease inhibitor (drug interaction with rifapentine)
- 6) No known porphyria
- 7) Not pregnant (women only).

Enrolled participants will undergo block stratified randomization, stratifying on four factors: a) CD4 <350 (if HIV+); b) HCV Ab status; c) ART status; and d) opioid dependence. After randomization and allocation to 12HR or 26H, participants will be provided 12HR weekly (12 weeks) and 26H daily (26 weeks) as directly observed therapy. Every 4 weeks, patients will be monitored for AST/ALT, adverse side effects and pregnancy. Premature treatment discontinuation will occur for any DAIDS Grade 4 toxicity, patient refusal to continue, or pregnancy (women only).

Study Design: TB Studies

Legend: LTBI=latent TB infection; H=isoniazid; HP=isoniazid + rifapentine; MMT= methadone maintenance treatment; BPN/NLX= buprenorphine/naloxone; OAT=opioid agonist treatment; ART= antiretroviral therapy; HCV= hepatitis C virus.

Part C:

A two-arm **preference trial** (no MAT, and methadone) of prisoners with opioid use disorders who are not or are currently being treated for TB and/or HIV, and are about to transition to the community and need to continue their treatment post-release. Patients may or may not be returning to Klang Valley and within 25 km of our research site. We anticipate enrolling 25-50 participants per arm.

Once consented, study participants will be provided an informed decision-making aid that will help them decide if medication-assisted treatment, specifically Methadone, is best for them. Participants will also have the option not to enroll in medication-assisted treatment.

[figure not shown]
Informed decision-making aid:

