Shared decision-making (SDM) is based on the principles of informed consent and patient-centered care, and involves patients actively partnering with their clinicians to make decisions that balance the best evidence for treatment with their personal values and preferences. Such tools using validated formal criteria have been developed in a wide variety of clinical contexts (e.g. cancer screenings, elective surgery, end-of-life care) to help guide patients in weighting risks, benefits and clarifying their values. These tools have demonstrated improved quality of decisions, satisfaction and some clinical outcomes. No such SDM tool exists in OUD treatment, and we ultimately aim to develop such a tool, pilot and evaluate its effect on clinical outcomes, especially in the initiation of and retention in OUD treatment after release from prison. At this time we will conduct focus group discussions to assess what baseline concerns, knowledge, and attitude participants have towards methadone maintenance therapy (MMT) and buprenorphine /naloxone (BPN/NLX). Although BPN/NLX is not new to Malaysia and not yet offered in prison by Ministry of Health, we will give a brief overview of BPN/NLX to the participants prior to the group session. This group discussion will guide the development of the SDM tool that will be used to help prisoners with OUDs decide if MMT is the best option for them.

We will conduct a specialized type of focus group, specifically nominal group technique (NGT), in which participants generate responses to a question and also rank the relative importance of these responses. Written notes as well as audio recording will be made. Groups will be voluntary and **anonymous**. We will collect demographic information of group participants that will be de-identified, aggregated and decoupled from any individual responses. Data will be analyzed qualitatively for themes as well as quantitatively for frequency of themes and relative rankings across all groups. This data will reveal some of the concerns and beliefs that patients have regarding MAT on presentation and their relative importance in treatment decision making.

We will recruit adults with OUDs from CCSC Kerinchi (community MMT site), Ikhlas (needle/syringe exchange program) and from Kajang prison. Group sessions will last no longer than 1 hour, and will include 6-10 participants per session. Groups will be conducted until a

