saturation of themes is reached. Participants will undergo informed consent prior to participating, and will be compensated 50RM for their time.

Upon making an informed decision using the SDM developed from the focus groups, those that choose methadone maintenance treatment (MMT) will initiate 5 mg of methadone, 3-4 months prior to release from prison. The dose will increase in 5 mg increments every 7 days (as tolerated) until the daily dose is escalated to at least 80 mg or optimal dose before the date of release. Patients prescribed MMT will receive medication daily in prison, and will receive their medications weekly in form of take-way dosing. MMT will be dispensed at the community research site. All participants will be maintained on medication-assisted treatment and will receive follow-up care for 6 months after release from prison.

After a baseline assessment, our research assistant (RA) would meet the participant at the prison on the day of release to undergo a brief assessment, urine testing and to introduce the patient to our community research site to ensure that s/he can find the site after release and take the participant home so that our research assistants can know where the person is living/residing. This process will also improve trust between the research staff and the participant. Thereafter, all participants will be seen monthly, where they will undergo urine screening and be assessed for alcohol and drug use using timeline follow-back (TLFB), appointments for HIV and/or TB, adherence to HIV and/or TB medications, assessments of legal, employment, family issues using the Lite version of the Addiction Severity Index (ASI), depressive symptoms, health-related quality of life (HRQoL), satisfaction with their treatment. They will also be assessed for diversion (and urine testing).

The primary outcome will be the proportion completing treatment for active or LTBI. Secondary analyses will compare Kaplan Meier curves using Cox proportion hazards and time to discontinuation. TB treatment adherence will also be measured using MEMS caps and analyzed as we have done previously in TB patients in Ukraine

Eligibility for Part C includes:

- 1) Meets inclusion for part A, if possible
- 2) Opioid dependence
- 3) Has LTBI or active TB disease (based on screening in Part A), or no TB
- 4) Returning to live in Kuala Lumpur/Klang Valley region (within 25 km of Kerinchi research site), if possible
- 5) ≤ 6 months before end of sentence

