Part A: New intakes from Kajang Prison will be recruited (80-120) per day. Mandatory HIV testing is done on all prisoners. HIV prevalence is 5%. All HIV+ prisoners upon entry will be approached for informed consent. For Part B, only prisoners who have >9 months (preferably 12 months) remaining on their prison sentence will be approached for recruitment. All subjects are expected to be Southeast Asians/Pacific Islanders. While women will represent only 10% of the sample, they will be included. The minimum age is 18 years of age, thus children 18-21 years old will be eligible for participation. Currently, only 2% of HIV+ prisoners are between 18-21 years. For part C, prisoners who have less than 90 days remaining on their prison sentence, but more than 90 days of TB treatment remaining will be approached for recruitment. They must be at least 18 years old, have latent TB infection defined by TST \geq 5mm (HIV+), or TST \geq 10mm (HIV-), return to live in Klang Valley (within 25 km of Kerinchi research site), and AST/ALT <5 X ULN.

Aim 2 will not include Human Subjects. Data analysis only.

6. Subject classification: Check off all classifications of subjects that will be specifically recruited for enrollment in the research project. Will subjects who may require additional safeguards or other considerations be enrolled in the study? If so, identify the population of subjects requiring special safeguards and provide a justification for their involvement.

 Children	 Healthy	 Fetal material, placenta, or dead fetus
 Non-English Speaking	 Prisoners	 Economically disadvantaged persons
 Decisionally Impaired	 Employees	 Pregnant women and/or fetuses
 Yale Students	 Females of childbearing potential	

NOTE: Is this research proposal designed to enroll children who are wards of the state as potential subjects? Yes No (If yes, see Instructions section VII #4 for further requirements)

7. Inclusion/Exclusion Criteria: What are the criteria used to determine subject inclusion or exclusion?

Inclusion and Exclusion Criteria:

1a: inclusion:

- Above 18 years old
- Malaysian Citizen
- Newly admitted (<2 days)
- Able to provide consent
- Absence of active TB within 2 years of enrollment

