- \geq 3 month prison sentence

1b inclusion:

- Meets inclusion criteria for part A
- Has latent TB (HIV+, or TST \geq 10mm (HIV-)) and no active TB disease
- >6 months before end of sentence to ensure option for treatment completion

- AST or ALT <5X ULN, or AST/ALT <3x ULN if TBil >2x ULN
- Not on a protease inhibitor (drug interaction with rifapentine)
- No known porphyria
- Able to provide informed consent

1c inclusion:

- Meets inclusion criteria for Part A, if possible
- Opioid dependence
- Has latent TB (HIV+, or TST \geq 10 mm (HIV-)), or active TB infection, or no TB
- Returning to live in Kuala Lumpur/Klang Valley region (within 25 km of Kerinchi research site), if possible
- AST/ALT <5X normal
- \leq 6 months remaining in prison
- Able to provide informed consent

Exclusion Criteria: Pregnant women or women planning to become pregnant will be excluded if we implement methadone or buprenorphine during pregnancy, the infant born to the mother is highly (>60%) likely to develop an infant abstinence syndrome that is avoidable by not providing MMT. If a woman becomes pregnant during the course of the study, MMT will not be discontinued if she is receiving it as withdrawal has resulted in pre-term labor. For women preferring not to be OAT, but who relapse to drug use, entry onto MMT will not be an exclusion criteria for remaining in the study.

8. How will **eligibility** be determined, and by whom?

Eligibility will be determined by the Research Assistants (RAs) hired by the University of Malaya – CERIA to work on this study. An eligibility screening form will be developed into REDCap, a data collection and management application that will be used by the local RAs.

Prior to enrollment, laboratory testing will be completed to ensure normal LFTs and urine testing will be completed to ensure that female participants are not pregnant.

9. **Risks:** Describe the reasonably foreseeable risks, including risks to subject privacy, discomforts, or inconveniences associated with subjects participating in the research.

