For patients in Aim 1, Part B (trial of 26H vs 12HR) and Part C (MMT, vs. no MAT), patients will be seen monthly clinically for symptoms of hepatitis or neuropathy and LFTs shall be monitored. Anyone whose LFTs increase to $>5X$ ULN, or $>3X$ ULN with symptoms of jaundice, nausea or fatigue, will be stopped from receiving medications and LFTs will be monitored weekly to ensure that LFTs are decreasing. Similarly, if patients develop Grade 3 or higher peripheral neuropathy, they will be discontinued. Of note, LFTs will be measured at baseline and monthly for 3 months for 12HR and monthly x 6 months for 26H.

MMT patients will be seen daily for the first month and may have their medications dispensed less frequently if they have no evidence of using illicit drugs by self-report or urine testing.

11. Data and Safety Monitoring Plan: Include an appropriate Data and Safety Monitoring Plan (DSMP) based on the investigator's risk assessment stated below. (Note: the HIC will make the final determination of the risk to subjects.) For more information, see the Instructions, page 24.

- a. What is the investigator's assessment of the overall risk level for subjects participating in this study?
- b. If children are involved, what is the investigator's assessment of the overall risk level for the children participating in this study?
- c. Include an appropriate Data and Safety Monitoring Plan. Examples of DSMPs are available here <http://www.yale.edu/hrpp/forms-templates/biomedical.html> for
 - i. Minimal risk
 - ii. Greater than minimal

Aim 1parts (a-c) requires a DSMB.

Data and Safety Monitoring Board

We will comprise a full Data and Safety Monitoring Board (DSMB), that will include three voting members from colleagues in the field. The PI on this grant is familiar with the implementation of a DSMB; he is currently serving as one of the board members of the NIDA Clinical Trials Network studies examining routine HIV testing among drug users.

The key elements of a DSMB include the following:

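### Part C's residence rule is mandatory in one section and optional in three other places, and the analysis makes no allowance for distance, which may bias OAT versus no OAT in either direction

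*Combined protocol and SAP*

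**What the plan says.** The residence condition for Part C appears in four places.

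- **Section V.3, Part C description:** "Patients may or may not be returning to Klang Valley and within 25 km of our research site".
- **Section V.3, eligibility list for Part C, and Section V.7, 1c inclusion:** "Returning to live in Kuala Lumpur/Klang Valley region (within 25 km of Kerinchi research site), if possible".
- **Section V.5, Subject Population:** the sentence on Part C opens "They must be at least 18 years old, have latent TB infection defined by TST" and ends "return to live in Klang Valley (within 25 km of Kerinchi research site), and AST/ALT <5 X ULN". The opening verb governs the whole list, so residence is a requirement here.

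Sections V.12, VII.3(a) and VII.3(c) also describe Part C eligibility or recruitment, without a residence rule.

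On methadone after release, Section V.3 says "MMT will be dispensed at the community research site" and that patients "will receive their medications weekly in form of take-way dosing". Section V.10 says "MMT patients will be seen daily for the first month and may have their medications dispensed less frequently", without stating whether this is in prison or in the community.

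On the comparison, the participant chooses after using a decision aid, and 25 to 50 per arm are expected (V.3). Section V.12 sets those choosing no OAT against those on OAT. The primary outcome is the proportion completing treatment for active or latent TB. Attrition of 15-20% is expected and missing counts as failure. No covariate adjustment is stated for Part C, whereas the Part B paragraph of the same section does plan to control for confounders.

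**The concern.** Under the Section V.5 wording, everyone in Part C lives near the site and distance can vary little. Under the other wording, people returning anywhere may enrol. Screening staff cannot apply both, and the Part C population is not defined until one is chosen.

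Under the optional wording, distance becomes a possible common cause of arm and outcome. A participant who expects to live far from the named dispensing place may be less inclined to choose methadone. The same person may be harder to retain, and with missing counted as failure a lost participant becomes a non-completer. A difference in completion between the arms could then partly reflect where people live. With 25 to 50 per arm, this is hard to separate afterwards if distant residents sit mostly in one arm.

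Unlike most influences on preference, distance can be known before the choice, needs one data field, and is let in by the wording of an eligibility rule.

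**Working it through.** **Text comparison.** The optional wording in V.3 and V.7 and the neutral wording in the V.3 description are compatible with each other: neither excludes a distant resident. Section V.5 does. The conflict is therefore one mandatory statement against three optional ones.

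**Timing.** Section V.3 has methadone starting 3-4 months before release. The only described step at which staff learn the home address is the journey home on release day. Screening against the residence criterion would mean asking about intended residence, but no section says the answer is recorded as data before the choice.

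**No stated figure to reproduce.** The Part C plan gives no alpha, power, completion rate or effect size. What follows is illustration.

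**Assumed inputs (none from the documents unless noted):**
- true completion 70% in both arms, so no OAT effect
- attrition 15% within 25 km (the lower end of the plan's 15-20%)
- attrition *a* beyond 25 km, the same in both arms
- share beyond 25 km: 5% in OAT, *f* in no OAT
- missing = failure (from V.12)

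**Formula.** Observed completion in an arm with share *s* beyond 25 km = 0.70 × [1 − ((1 − s) × 0.15 + s × a)]. The spurious difference (OAT minus no OAT) is 0.70 × (f − 0.05) × (a − 0.15).

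**Central case, f = 0.40, a = 0.50:**
- OAT attrition: 0.95 × 0.15 + 0.05 × 0.50 = 0.1675; completion 0.70 × 0.8325 = 58.3%
- no-OAT attrition: 0.60 × 0.15 + 0.40 × 0.50 = 0.29; completion 0.70 × 0.71 = 49.7%
- difference: 0.70 × 0.35 × 0.35 = 0.086, or 8.6 points

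**Range, f from 0.30 to 0.50 and a from 0.40 to 0.60:**
- low: 0.70 × 0.25 × 0.25 = 0.044
- high: 0.70 × 0.45 × 0.45 = 0.142

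This is about 4 to 14 points.

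**Check against the plan's attrition (equal arms).** Central case: (16.75% + 29%) / 2 = 22.9%. Top of the range: (17.25% + 37.5%) / 2 = 27.4%. Bottom: (16.25% + 22.5%) / 2 = 19.4%. Only the bottom lies within 15-20%. If average attrition is held at 20% with 15% within 25 km, then (a − 0.15) × (f + 0.05) = 0.10 and the difference is 0.07 × (f − 0.05) / (f + 0.05). That is 5.0 points at f = 0.30 and 5.7 points at f = 0.50.

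**Direction.** Swapping the shares (40% of OAT and 5% of no OAT beyond 25 km) gives 8.6 points against OAT. Equal shares give zero.

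**Effect on the test.** As a separate assumption, take 70% completion near the site, 20 points lower far away, with 0% of OAT and 50% of no OAT far away. The expected rates are 70% and 60% with no OAT effect. A nominal two-sided 5% test (normal approximation) then rejects in 11.4% of trials at 25 per arm and 18.1% at 50 per arm. For scale, with base completion of 30-60%, the difference detectable with 80% power is about 33-39 points at 25 per arm and 25-28 points at 50 per arm.

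**The case against.** A reader might infer something stronger: that methadone is available only at Kerinchi, so distance decides who can choose it, distant residents fill the no-OAT arm, and the result is tilted toward OAT. The documents do not support this.

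- Section V.3 names the community research site but does not exclude others, and Section V.9 describes methadone as part of routine clinical care.
- No section makes the choice depend on distance. Methadone starts in prison, so a distant resident can choose and begin it, and weekly take-away supply would reduce travel. The daily attendance in V.10 may fall before release. Because its place is not stated, it needs reconciling with the weekly supply in V.3.
- Participants are seen monthly, but the place is not named, and nothing says TB treatment is delivered at Kerinchi.
- If distant residents choose methadone and then drop out, missing = failure counts against OAT.

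It can also be said that Section V.5 looks like one paragraph left unrevised. It differs from V.3 and V.7 on time to release (under 90 days against 6 months or less) and on TB status (latent infection required against no TB allowed). That is plausible, but correcting it to the optional wording leaves distance unhandled in the analysis.

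Further, Part C is openly self-selected, distance is one of many possible confounders, and the plan has retention measures: mobile phones with calling minutes (VII.3) and payment toward time and transport for post-release interviews (X.2). These points stand, and they limit the size of the concern. They do not balance distance between arms or replace a planned adjustment.

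**Conclusion.** The contradiction is certain: Section V.5 makes residence within 25 km a requirement and V.3 and V.7 do not. That distance may confound OAT versus no OAT is credible and not handled by the plan. That it does so, by how much and in which direction cannot be derived from the documents.

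The 8.6 points, and the range of about 4 to 14, rest wholly on assumed shares and attrition. Most of that range implies more attrition than the plan expects; at 20% average attrition with 15% within 25 km, the figure is 5 to 6 points. This is well below the difference the trial could reliably detect, so the main harm is a shifted estimate and an uncertain interpretation. The bias vanishes if distance is balanced between arms and acts alike in both, or is unrelated to completion. It should be put right because the repair is cheap and works only if the information is collected before the choice.

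**What to change.** 1. Reconcile Section V.3 (Part C description and eligibility list), Section V.5 and Section V.7 (1c) to one residence rule applied to both arms. Which rule is the sponsor's choice.
2. Record intended residence, or distance to the site, at baseline and before the OAT choice.
3. In Section V.12, pre-specify stratification or adjustment of the primary Part C comparison by within or beyond 25 km, with a sensitivity analysis limited to participants returning within 25 km. If the mandatory rule is kept and was applied throughout, the outer stratum is empty and this step falls away.

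Limiting the primary comparison itself to those within 25 km is a defensible alternative, but it shrinks a set of only 25 to 50 per arm, so it fits better as the sensitivity analysis.

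The cost is protocol wording, one baseline field and a little more analysis. Adjustment will do little if nearly all distant residents fall in one arm. In that case the within-25-km analysis should be given prominence when the results are interpreted.
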